7.8. Criteria for Adverse Events of Specific Concern and Dose Adjustment

The National Cancer Institute's (NCI's) Common Terminology Criteria for Adverse Events (CTCAE), Version 5.0, will be used for grading toxicities, except for CRS, which will be graded using the CRS revised grading system (Section 11.2 or Appendix C; Lee, 2014).

An AESC is defined as an AE or clinically significant abnormal laboratory value (unless clearly attributable to underlying malignancy or concurrent disease) occurring after the initiation of dosing and meeting the criteria listed below:

For Parts A, B, and C:

1. Any Grade 5 toxicity

Version 1.0 Page 51 of 145

- 2. Grade \geq 3 thrombocytopenia lasting \geq 7 days or \geq Grade 3 thrombocytopenia of any duration if associated with \geq Grade 3 bleeding
- 3. Grade 4 neutropenia or Grade 3 febrile neutropenia lasting ≥ 7 days, or Grade 4 febrile neutropenia
- 4. Any \geq Grade 3 nonhematological toxicity, **except**:
 - a. Grade 3 fatigue, asthenia, fever, anorexia, or constipation
 - b. Grade 3 nausea, vomiting, diarrhea, or abdominal pain controlled by medical management that decreases to \leq Grade 2 within \leq 7 days
 - c. Grade 3 alanine aminotransferase (ALT) and/or aspartate aminotransferase (AST) that decrease to \leq Grade 2 within \leq 5 days
 - d. Grade ≥ 3 gamma glutamyl transferase (GGT), unless it occurs with AST, ALT, and/or total bilirubin values that meet AESC criteria
 - e. Grade 3 electrolyte abnormalities that are clinically insignificant, or treatable, and that resolve, with or without intervention, to < Grade 2 in < 72 hours
 - f. Grade 3 or 4 lipase values that are not accompanied by ≥ Grade 3 amylase values or clinical symptoms or radiographic evidence of pancreatitis

Additional Criterion for Part B (combination therapy) only:

1. Any immune related adverse event (IRAE) that requires permanent discontinuation of study drug according to the guidelines in Table 18

Subjects who experience any toxicity should be followed until the toxicity stabilizes or has returned to their baseline level, or until the commencement of a new anticancer treatment.

Refer to Section 10.3 for safety criteria for adjustment or stopping XmAb18087 and pembrolizumab.

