7.9. Study Assessments

The Schedule of Assessments is shown in Table 7. Pretreatment, treatment, and follow-up procedures are detailed in Sections 7.9.1 through 7.9.5.

Version 1.0 Page 53 of 145

Table 7: Schedule of Assessments

Evaluation or Procedure	Pretrea	tment							Cycle	e 1						
Study Day	Screen (-28 to -2)	Day -1	1	2	3	8	9	10	15	22	29	36	37	38	39	40 ± 2
Informed consent	X															
NETSPOT Gallium 68 dotatate PET/CT scan ^{a,b}	X															X
Review of inclusion/exclusion criteria	X															
Collection of FFPE tumor sample/slides	X															
Record tumor genetic information	X															
Inpatient status ^{c,d}		X	X	X	X	X	X	X				X	X	X	X	
XmAb18087 administration ^{e,f}			X			X			X	X	X	X				
Pembrolizumab administration ^f									X							
Medical history ^g	X	X														
Demographics	X															
Physical examination ^{g,h}	X	X		X	X	X	X	X	X	X	X	X				X
Neurologic examination ⁱ		X														
Vital signs ^{c,j,k}	X	X	X	X	X	X	X	X	X	X	X	X	X	X	X	
Height		X														
Weight		X	X			X			X	X	X	X				
ECOG performance statush	X	X	X			X			X	X	X	X				
12-lead electrocardiogram (supine) ^{l,m}	X	X	X			X	X		X	X	X	X				
CBC w/ differential (absolute and percentage), platelet count ^h	X		X	X	X	X	X	X	X	X	X	X				
Chemistry panel ^h	X		X	X	X	X	X	X	X	X	X	X				
Coagulation panelh	X		X	X		X		X	X	X	X	X				
Urinalysis	X	X		X		X		X	X	X	X	X				
HBsAg, HBcAb, HCV, HIV	X															

Version 1.0 Page 54 of 145

Table 7: Schedule of Assessments (Continued)

Evaluation or Procedure	Pretrea	itment							Cycle	: 1						
Study Day	Screen (-28 to -2)	Day -1	1	2	3	8	9	10	15	22	29	36	37	38	39	40 ± 2
Serum β–hCG (females of childbearing potential) FSH (postmenopausal) ⁿ	X	X								X						
Flow cytometry (blood) ^o			X	X	X	X	X	X	X	X	X	X	X	X	X	
Cytokine/inflammation panel ^p			X	X	X	X	X	X	X	X	X	X	X	X	X	
Polyoma virus assay (serum) ^q		X														
Biobanking sample (blood) ^{r,s}		X		X		X										X
PK blood sampling ^t		X	X	X	X	X		X	X	X	X	X	X	X	X	
Immunogenicity (ADA) blood sampling ^u		X	X			X			X	X	X	X				
RECIST 1.1 tumor assessment ^v	X															X
Monitor/record adverse events	X	X	X	X	X	X	X	X	X	X	X	X	X	X	X	X
Concomitant medications	X	X	X	X	X	X	X	X	X	X	X	X	X	X	X	X
Fresh tumor biopsy (optional) ^{s,w}	X							X								

Version 1.0 Page 55 of 145

Table 7: Schedule of Assessments (Continued)

Evaluation or Procedure			C	ycle 2 and	Higher		
Study Day	1	8	15	22	29	36	40 ± 2
NETSPOT Gallium 68 dotatate PET/CT scan ^{a,b}							X

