Version 1.0 Page 57 of 145 Abbreviations: ADA = anti-drug antibody; β–hCG = beta unit of human chorionic gonadotrophin; CBC = complete blood counts; CT = computed tomography; EOI = end of infusion. EOT = end of treatment; ECG = electrocardiogram; ECOG = Eastern Cooperative Oncology Group; FACS = fluorescence-activated cell sorting; FFPE = fresh frozen paraffin-embedded; FSH = follicle-stimulating hormone; HBsAg = hepatitis B surface antigen; HBcAb = hepatitis B core antibody; HCV = hepatitis C virus; HIV = human immunodeficiency virus; mo = month; MRI = magnetic resonance imaging; NET = neuroendocrine tumors; PE = physical examination; PET = positron emission tomography; PK = pharmacokinetic; RECIST = Response Evaluation Criteria In Solid Tumors; SSTR2 = somatostatin

- ^a If subject has undergone NETSPOT gallium 68 dotatate PET/CT scan within 6 weeks prior to enrollment and the images and a report of results are available for collection, the scan need not be repeated at baseline. If SSTR2 radionuclide scanning and RECIST 1.1 tumor assessment by CT/MRI are planned within 2 days of each other. RECIST imaging should be conducted first.
- b NETSPOT gallium 68 dotatate PET/CT scan will be performed on Day 40 ± 2 of Cycle 1 and of every second cycle thereafter; that is, at the end of Cycle 3, Cycle 5, etc. The EOT scan will be performed only if the subject has not undergone scan within the past 2 months.
- ^c On Day -1, hospitalization is optional. Hospitalization on Days 36 through 39 in Cycle 1 is optional if PK sampling cannot be accommodated as an outpatient. Vital sign assessments on Days 36 through 39 in Cycle 1 will be performed only if the subject is hospitalized.
- d Any subject who has shown symptoms of CRS during a required inpatient hospitalization will be monitored as an inpatient for at least 24 hours after the symptoms have subsided.
- EXMAb18087 will be administered as be observed as inpatients for the first 2 doses. For all other infusions of XmAb18087, the subject will be observed for at least 4 hours following subsequent infusions, except that the observation period may be decreased to 2 hours if no infusion reactions have occurred for at least 3 consecutive infusions and the subject has completed 4 infusions at the highest dose for that subject.

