- f XmAb18087 is administered on Day 15 in Parts A and C only. Pembrolizumab is administered on Day 15 of each cycle in Part B only. XmAb18087 is NOT to be administered on Day 15 in Part B. Pembrolizumab will be provided by sites as standard of care.
- g Complete medical history and PE is to be performed at Screening. For all the other time points, only an abbreviated, symptom-directed PE is to be performed.
- May be performed up to 24 hours prior to infusion. The following procedures that are completed on Day -1 within 24 hours of Cycle 1 Day 1 dosing do not need to be repeated on Cycle 1 Day 1: PE, ECOG, and local safety laboratories (eg, CBC with differential and platelets, chemistry panel, coagulation panel, and urinalysis). These safety laboratory assessments will be performed by the central laboratory and should also be performed by local clinical site laboratories so that clinical site personnel can review results before administering XmAb18087.
- Baseline neurologic examination to be performed on Day -1. If a subject appears to be experiencing neurologic toxicity, the neurologic examination should be repeated as necessary to evaluate the subject's condition. Guidelines on management of neurologic toxicity are included in both Section 11.3.3.4 and Appendix C.
- Supine blood pressure and pulse rate, body temperature, respiratory rate, and blood oxygen saturation by pulse oximetry. On days of XmAb18087 infusions, vital signs should be taken within 60 minutes of predose; 15, 30, and 60 minutes after start of infusion (± 5 minutes for each time point); immediately (within 5 minutes) before EOI; 15, 30, and 60 minutes after EOI (± 5 minutes for each time point); and then hourly (± 5 minutes) for 3 hours. When possible, vitals should be measured before blood sampling. Oxygen saturation levels will be captured with each vital sign collection; however, pulse oximetry monitoring must be maintained continuously throughout the entire admission or observation period for each administration of XmAb18087. For information on management of oxygen saturation of 90% or lower, see Section 11.3.3.1. All vital signs during infusion should be taken with the subject in the same position. On nondosing days, vitals should be measured before blood sampling.

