10.1.2. Prophylaxis of Nausea and Vomiting

are recommended for treatment of the symptoms.

Sites may also choose to use other or additional antinausea/vomiting medications for prophylaxis or treatment of symptoms, according to their practice and assessment of the subject's responses.

10.1.3. Prophylaxis of Infusion Reactions/Cytokine Release Syndrome:

It is also required that all subjects receive the following medications before at least the first 4 doses the of study drug:

- a. Acetaminophen (Tylenol®): 650 mg PO once before dosing with XmAb18087
- b. Diphenhydramine (Benadryl®): 50 mg PO once before dosing with XmAb18087
- c. 10 to 20 mg IV dexamethasone (Decadron®) before dosing with XmAb18087

If a subject receives 4 consecutive doses of XmAb18087 without \geq Grade 1 infusion reaction or CRS, the prophylaxis described above may be modified, including elimination and/or reduced doses of some required medications.

For guidelines on the treatment of infusion reactions and CRS, see Section 11.2 or Appendix C of this protocol.

If at all possible, infusions of XmAb18087 should start before 2 PM local time. This is especially important for the C1D1 and any first dose at an escalated level to ensure that adequate staffing and services are available to manage a severe episode of CRS. In addition, either a Principal

Version 1.0 Page 73 of 145

Protocol XmAb18087-02

Investigator or subinvestigator (MD) must be readily available during, and for a minimum of 24 hours after, administration of an XmAb18087 dose.

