Cytokine release syndrome, on the other hand, is more likely to occur after the first dose or first escalated dose of drug than after subsequent doses. It may begin somewhat later and is more likely to be associated with hepatic and neurologic complications, including the following:

- Any of the hypersensitivity signs or symptoms listed above
- Aphasia or word-finding difficulty
- Elevated d-dimer and/or hypofibrinogenemia
- Fatigue (asthenia, lethargy, malaise)
- Gait disturbance/dysmetria
- Hallucinations
- Seizures
- Transaminitis and/or hyperbilirubinemia
- Tremor

The Xencor Medical Monitor should be contacted immediately if questions arise concerning the grade and/or treatment of the infusion reaction.

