11.3.3. Treatment Guidelines for Cytokine Release Syndrome

11.3.3.1. Use of Tocilizumab for Cytokine Release Syndrome

Tocilizumab is a therapeutic antibody that interferes with binding of IL-6 to the IL-6 receptor. It has been used to decrease the severity and possibly mortality of severe CRS (Frey, 2017), and early administration may be useful in improving outcomes. Below are suggested guidelines for its use:

Version 1.0 Page 88 of 145

- Sufficient tocilizumab (dose of 8 mg/kg) should be readily available to the area where subjects are receiving their infusions and being observed post infusion.
- Prompt tocilizumab therapy should be strongly considered if:
 - Oxygen saturation falls below 90% on room air, **OR**
 - Systolic blood pressure falls 20 mm Hg below predose measurements and below 100 mm Hg, **OR**
 - Temperature of > 38 °C (100.4 °F) in the presence of new or worsening dyspnea and/or tachypnea and/or rigors and/or tachycardia (heart rate [HR] > 110 bpm), OR
 - Early discovery of hepatic transaminase elevation. (Note that peak transaminase elevation appears to occur within 24 hours, so that it is unlikely that tocilizumab treatment on the day after study drug administration would affect the course or outcome in the absence of concurrent symptoms or signs of CRS).
- Repeat dosing of tocilizumab may be necessary if signs and symptoms persist or return after initial treatment.

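### No chemistry is scheduled for 6 to 7 days after the first 2.0 and 4.0 µg/kg doses, so an early, transient liver-enzyme rise at these levels may be missed

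*Protocol*

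**What the plan says.** **Timing of risk.** Protocol Section 11.3.2 states that CRS "is more likely to occur after the first dose or first escalated dose of drug than after subsequent doses", and its list of complications includes transaminitis. Section 10.1.3 asks for infusions to start before 2 PM so that staff are on hand for a severe CRS episode, and adds: "This is especially important for the C1D1 and any first dose at an escalated level". Section 11.3.3.1 says: "Note that peak transaminase elevation appears to occur within 24 hours". The same section lists early discovery of raised transaminases among the reasons to consider tocilizumab promptly.

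**Sampling.** In Table 7 (Section 7.9) the "Chemistry panel" row is marked in Cycle 1 on Days 1, 2, 3, 8, 9, 10, 15, 22, 29 and 36, with nothing on Days 37 to 39. Footnote h says of these tests: "May be performed up to 24 hours prior to infusion". It also says that local results are there for review before XmAb18087 is given, so a dosing-day sample does not assess that day's dose.

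**Observation.** Footnote e has subjects "be observed as inpatients for the first 2 doses". Later infusions carry at least 4 hours of observation.

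**Counting rule.** Section 7.8 makes most nonhematological toxicity of Grade 3 or higher an AESC. It excepts "Grade 3 alanine aminotransferase (ALT) and/or aspartate aminotransferase (AST) that decrease" to Grade 2 or lower within 5 days. Grade 4 ALT or AST is not excepted.

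**The concern.** The 24- and 48-hour chemistry follows only the two lowest-dose exposures. The levels that the safety run-in exists to judge, 2.0 and 4.0 µg/kg, have no scheduled chemistry until just before the next weekly visit. If the protocol is right that a transaminase rise peaks within a day, the scheduled samples are badly timed to see it.

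Three sets of rules depend on seeing it. Section 7.7 decides from AESC counts whether a cohort of 3 grows to 6 or pauses for the Safety Review Committee (SRC), so one uncounted event in three changes the path. Section 10.3.1 holds dosing after an AESC and bars rechallenge after Grade 4 toxicity. The recommended dose is then chosen from the same data. Because early sampling is present up to 1.0 µg/kg and absent above it, liver-enzyme toxicity may be under-ascertained at the higher doses, which would flatter them in any comparison across levels.

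**Working it through.** **Step 1. Cross the dose tables (Tables 2 to 4) with the chemistry row of Table 7.** Gap = day of next scheduled chemistry minus day of first exposure. Where the next sample is a pre-dose one, it may be drawn 24 hours early, so 7 days can become 6.

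| Cohorts | First dose at | Study day | Next chemistry | Gap, days | Required observation |
|---|---|---|---|---|---|
| All | 0.3 µg/kg | 1 | Day 2 | 1 | inpatient |
| All except 1B | 1.0 µg/kg | 8 | Day 9 | 1 | inpatient |
| 2A, 3A, 2C, 3C | 2.0 µg/kg | 15 | Day 22 | 6–7 | at least 4 h |
| 3A, 3C | 4.0 µg/kg | 22 | Day 29 | 6–7 | at least 4 h |
| 3B, 4B | 2.0 µg/kg | 29 | Day 36 | 6–7 | at least 4 h |
| 4B | 4.0 µg/kg | 50 (Cycle 2 Day 8, Table 3) | Day 57 | 6–7 | at least 4 h |

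Every first dose at 2.0 or 4.0 µg/kg has the 6–7 day gap. Cohorts 1A, 1C, 1B and 2B do not exceed 1.0 µg/kg and are unaffected at their assigned dose. For 4B, the synopsis text lists Day 1 of later cycles under both 2.0 and 4.0 µg/kg, which disagrees with Table 3 and must be reconciled.

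**Step 2. Compare the gap with the protocol's own times.** A 6–7 day gap is longer than the 24-hour peak and longer than the 5-day AESC window. Taking the cases in turn:

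- Grade 3 that falls to Grade 2 or lower within 5 days: excepted, so missing it loses no AESC.
- Grade 3 that lasts more than 5 days but is gone by the next draw: an AESC, not counted. The window is narrow, at most 7 − 5 = 2 days.
- Brief Grade 4: an AESC, not counted if it resolves before the next draw.
- Grade 3 found at the next draw: seen, but its onset is unknown, so the time already spent at Grade 3 cannot be set against the 5 days.

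**Step 3. Illustrate the size.** The documents give a peak time but no peak height and no rate of fall. Assume a peak at 24 hours and halving every h = 1, 2 or 3 days. The value at the next draw is peak × 2^(−6/h) for a draw on day 7, and peak × 2^(−5/h) for a draw on day 6. Values are multiples of the upper limit of normal (ULN).

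| Peak | Draw | h = 1 | h = 2 | h = 3 |
|---|---|---|---|---|
| 10 | day 7 | 0.16 | 1.25 | 2.5 |
| 10 | day 6 | 0.31 | 1.8 | 3.1 |
| 20 | day 7 | 0.31 | 2.5 | 5.0 |
| 20 | day 6 | 0.62 | 3.5 | 6.3 |

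For reference, Section 8.6 excludes subjects without known liver metastases at 3 × ULN or above. On day 7, with halving every 2 days or faster, both peaks read below 3 × ULN. With slower fall or an earlier draw, some remain visible.

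**The case against.** Much of the case on the other side is sound.

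- **The Section 11.3.2 sentence alone shows no conflict.** It speaks of one first escalated dose. Read literally, that is Day 8 in every cohort except 1B, and Day 8 has admission and Day 9 and 10 chemistry. Section 5.1.7 expects CRS principally after the first dose. The mismatch rests on Section 10.1.3, which names every first dose at a higher level, together with the peak time in Section 11.3.3.1. Section 10.1.3 is about start times and staffing, and it also requires a physician to be readily available for at least 24 hours after each dose.
- **A reader might infer that toxicity at 2.0 and 4.0 µg/kg goes unseen altogether.** The documents do not support that. Rises that persist appear at the next weekly draw and are then followed until stable (Sections 7.8 and 11.1.6). There are vital signs, continuous oximetry, post-infusion ECGs, cytokine draws to 7 hours after infusion on Days 15, 22 and 29, extra cytokine samples whenever CRS is suspected, and discretionary local tests (Section 11.5). None of these requires chemistry, so the gap in scheduled liver tests remains.
- **A reader might extend the point to blood counts.** No passage describes a short-lived cytopenia, and the hematologic AESCs in Section 7.8 rest mostly on a duration of at least 7 days or on bleeding or febrile neutropenia. Weekly counts suit most of them.
- **A rationale may exist.** Section 5.3, on dose selection and design, is redacted in the public copy.

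**Conclusion.** The point holds for liver enzymes only. After every first 2.0 or 4.0 µg/kg dose, scheduled chemistry is absent for 6 to 7 days, against a stated peak within 24 hours and a 5-day counting rule. Scheduled tests may miss an early, transient rise. The AESCs at stake are a brief Grade 4 rise and, in a window of at most 2 days, a Grade 3 rise that outlasts 5 days. The schedule facts are firm. The size of a missed rise is not: it rests on the assumed peak and rate of fall, and the slow end of the range is visible at the next draw.

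Reach in this trial is small. SAP Section 5.1 reports 4 subjects, 2 in Part A and 2 in Part C. With 3 subjects initially enrolled per cohort before the SRC convenes (Section 7.7), and intrasubject escalation tied to completion of the next cohort (Section 7.4.3), none should have gone above 1.0 µg/kg, though actual doses are not stated. The point is a modest, inexpensive improvement to the design.

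**What to change.** In Table 7, add the chemistry panel to Cycle 1 draws that already exist:

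- the 7-hour post-infusion cytokine draw on Days 15, 22 and 29, where that day is an XmAb18087 dosing day (Day 15 in Part B is pembrolizumab);
- the Day 37 and Day 38 draws, 24 and 48 hours after the Day 36 dose.

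State in the protocol that this is partial. Seven hours may come before the peak and says nothing about duration. Days 37 and 38 follow a repeat dose at the cohort's Cycle 1 maximum: the fourth 2.0 µg/kg dose in 2A and 2C, the third 4.0 in 3A and 3C, and the second 2.0 in 3B and 4B. The first 4.0 µg/kg dose in 4B, in Cycle 2, has no post-dose cytokine draw to attach to and stays uncovered.

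The cost is slightly more blood and laboratory expense, with no added visit, staff or procedure. Separately, the sponsor must reconcile the admission and observation text (Section 7.1 and Table 7 footnote e) with the escalated-dose risk text (Sections 10.1.3 and 11.3.2). Which clinical rule is right is not for this review to say.

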11.3.3. Treatment Guidelines for Cytokine Release Syndrome

11.3.3.1. Use of Tocilizumab for Cytokine Release Syndrome

Tocilizumab is a therapeutic antibody that interferes with binding of IL-6 to the IL-6 receptor. It has been used to decrease the severity and possibly mortality of severe CRS (Frey, 2017), and early administration may be useful in improving outcomes. Below are suggested guidelines for its use:

Version 1.0 Page 88 of 145

- Sufficient tocilizumab (dose of 8 mg/kg) should be readily available to the area where subjects are receiving their infusions and being observed post infusion.
- Prompt tocilizumab therapy should be strongly considered if:
 - Oxygen saturation falls below 90% on room air, **OR**
 - Systolic blood pressure falls 20 mm Hg below predose measurements and below 100 mm Hg, **OR**
 - Temperature of > 38 °C (100.4 °F) in the presence of new or worsening dyspnea and/or tachypnea and/or rigors and/or tachycardia (heart rate [HR] > 110 bpm), OR
 - Early discovery of hepatic transaminase elevation. (Note that peak transaminase elevation appears to occur within 24 hours, so that it is unlikely that tocilizumab treatment on the day after study drug administration would affect the course or outcome in the absence of concurrent symptoms or signs of CRS).
- Repeat dosing of tocilizumab may be necessary if signs and symptoms persist or return after initial treatment.

11.3.3.2. Fluid Management

Cytokine release syndrome is sometimes associated with myocardial dysfunction, pulmonary edema, or capillary leak syndrome (Shimabukuro-Vornhagen, 2018). Although there are little or no data regarding use of anti-CD3 antibodies and the need for fluid management, it seems prudent to monitor subjects for weight gain and limit IV fluid administration in the acute setting.

- If a subject is noted to have had a ≥ 10% increase in body weight over the previous 2 weeks in association with new or significantly increased bilateral lower extremity edema, dosing should be delayed until this finding is evaluated and, if indicated, treated.
- For acute hypotension, an IV fluid bolus should be limited to 500 mL of normal saline or the equivalent.
- If there is not an adequate response to fluids, treatment with tocilizumab (and vasopressors, if necessary) should be considered rather than additional fluid boluses.

